10.2 Endpoint definitions

In the semen analysis, we will include changes in the following parameters: Semen volume (ml), sperm concentration ($\times 10^6$), sperm motility (% progressive), sperm morphology (% normal forms) and sperm viability (% viable); as exploratory endpoints.

Total testosterone will be expressed in ng/dL, and FSH and LH in mIU/mL. Hormone determinations will be done by peripheral venous puncture blood draw.

10.3 Sample size, accrual and study duration

TOTAL SAMPLE SIZE: 80
TOTAL ACCRUAL: 80
ACCRUAL DURATION: 6 months
STUDY DURATION: 27 weeks

10.4 Statistical Analysis and Power calculation

The average and standard deviation of all relevant variables and baseline characteristics, primary and secondary outcomes will be calculated.

Change in sperm count will be analyzed using the ANOVA and MANOVA. A change in $< \pm 10\%$ will be reject the null hypothesis.

LH, FSH, E and Testosterone levels will be analyzed using one-sample t-test with repeated measures throughout the study.

IIEF-EF and SF-36 questionnaires will be analyzed and compared between the groups according to Fisher's exact test in each of the endpoints. The statistical significance will be set at $P < 0.05$.

Demographic characteristics such as age and testosterone level will be compared between groups A and B using student's test. Other demographic characteristics, such as medical background and risk factors will be compared between these groups using Fisher's exact test.

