2. HYPOTHESIS

2.1 Alternate hypothesis

Natesto™ will not change sperm count by $\pm 10\%$ from baseline.

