2.2 Null Hypothesis

Natesto™ will change sperm count by $\pm 10\%$ from baseline.

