3.2 Secondary Efficacy Objective

Secondary outcomes will be changes in sperm count from baseline, 14 weeks ± 7 days, and 26 weeks ± 7 days after treatment, as well as monitoring for adverse effects throughout the duration of our study.

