4. STUDY DESIGN

4.1 Accrual goal

A total of 40 patients with a diagnosis of idiopathic hypogonadism (testosterone <350 on two consecutive T samples collected 1-4 weeks apart. meeting the eligibility criteria will be recruited from the Department of Urology clinic.

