10. STATISTICAL CONSIDERATIONS

10.1 Primary Study Endpoints

The primary endpoint will be change in FSH, LH, Testosterone, and Semen Analysis after 6 months of treatment of Natesto.

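### Section 10.4 decides a ±10% equivalence hypothesis with difference tests and a bare cut-off; under the cut-off, a true 10% change passes as no change up to about half the time

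*Combined protocol and SAP*

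**What the plan says.** Section 2 contains one hypothesis pair. The alternative (2.1) is that the drug "will not change sperm count by" ±10% from baseline; the null (2.2) is that it "will change sperm count by" ±10%. Rejecting the null therefore means concluding that sperm count is preserved to within 10%.

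Section 10.4 gives the analysis: "Change in sperm count will be analyzed using the ANOVA and MANOVA". It adds that a change smaller than ±10% "will be reject the null hypothesis". It does not say whether this is the mean, the median or a per-patient change, or how the rule combines with the ANOVA. The 0.05 significance level appears in the paragraph on the questionnaires and is not linked to the ±10% rule. Although the section title promises a power calculation, no SD, power or expected change is given.

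Two other inconsistencies bear on the point:

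- **Status of the endpoint.** Section 3.2 says "Secondary outcomes will be changes in sperm count from baseline". Section 10.1 says "The primary endpoint will be change in FSH, LH, Testosterone, and Semen Analysis after 6 months of treatment of Natesto". Section 10.2 lists the semen parameters "as exploratory endpoints".
- **Sample size.** Section 4.1 plans "A total of 40 patients with a diagnosis of idiopathic hypogonadism"; sections 6.3 and 10.3 give 80.

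**The concern.** To reject a null of non-equivalence, the data must exclude changes of 10% or more. Neither element of 10.4 does that. ANOVA and MANOVA have zero change as their null: a significant result does not show that the change exceeds 10%, and a non-significant one does not show that it is smaller. The cut-off compares an estimate with the margin and ignores its sampling error, so an imprecise estimate of 9% counts the same as a precise one.

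The conclusion at stake is the one the study was set up to reach. Section 1.3 presents maintained spermatogenesis as the potential advantage of this product and says its effect on sperm count is unproven; section 8.1 warns that large doses may lower the count. Under the rule as written, the trial could report preserved sperm count while its own data are compatible with a fall beyond its own margin.

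**Working it through.** **Inputs from the plan.** Margin ±10% (2.1, 2.2, 10.4); n = 40 (4.1) or 80 (6.3, 10.3); nominal level 0.05 (10.4). The plan has no power figure to reproduce.

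**Assumptions.** The SD of the change is not given. I used an SD of log(week 26/baseline) of 0.3, 0.5 and 0.7, normality on that scale, and limits ln 0.9 = −0.1054 and ln 1.1 = 0.0953. The rule is read as applying to the observed mean change. All n are evaluable men, because no dropout rate is stated.

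**Step 1: error of the cut-off.** With true ratio r and SE = SD/√n,

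P(declare no change) = Φ((0.0953 − ln r)/SE) − Φ((−0.1054 − ln r)/SE).

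At r = 0.90 this becomes Φ(0.2007/SE) − Φ(0), which cannot exceed 0.50 whatever the SD or n. For example, SD 0.5 and n = 40 give SE = 0.0791, and Φ(2.54) − 0.5 = 0.494.

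| True change | n | SD 0.3 | SD 0.5 | SD 0.7 |
|---|---|---|---|---|
| 10% fall (margin) | 40 | 0.500 | 0.494 | 0.465 |
| 10% fall (margin) | 80 | 0.500 | 0.500 | 0.495 |
| 15% fall | 40 | 0.114 | 0.234 | 0.293 |
| 15% fall | 80 | 0.044 | 0.153 | 0.232 |

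On a percent-change scale with a much larger SD of 100 or 150 points, the probability at the margin is Φ(0) − Φ(−20/SE): 0.397 or 0.300 with n = 40, and 0.463 or 0.383 with n = 80. It falls there only because the estimate is so noisy that it often misses the interval altogether.

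**Step 2: the other readings of 10.4.** If a non-significant two-sided 5% one-sample t-test were read as no change, the probability at a true 10% fall (noncentral t) is 0.42, 0.75 and 0.85 with n = 40, and 0.13, 0.54 and 0.74 with n = 80, for SD 0.3, 0.5 and 0.7. If both non-significance and an observed change under 10% were required, SD 0.3 and n = 80 give 0.13. None of these holds the error at 0.05.

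**Step 3: an interval rule.** Reject only if the 90% CI, mean ± t(0.95, n−1) × s/√n, lies wholly inside the limits (two one-sided tests at 5% each). The probabilities are integrated over the sampling distribution of s.

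| Quantity | n | SD 0.3 | SD 0.5 | SD 0.7 |
|---|---|---|---|---|
| Error at a 10% fall | 40 | 0.044 | 0.0003 | 0.000 |
| Error at a 10% fall | 80 | 0.050 | 0.024 | 0.000 |
| Power, no true change | 40 | 0.334 | 0.0006 | 0.000 |
| Power, no true change | 80 | 0.809 | 0.115 | 0.000 |
| n for 80% power, no true change | – | 79 | 217 | 423 |

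The largest SD allowing 80% power is 0.212 at n = 40 and 0.303 at n = 80. The interval is wider than the limits once s exceeds 0.2007 × √n/(2t): 0.377 at n = 40 (t = 1.685) and 0.539 at n = 80 (t = 1.664).

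Zero true change is the favourable case. At a true 5% fall with SD 0.3, power at n = 80 is about 48%, and 80% power needs about 192 men.

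**The case against.** The strongest reply has four parts.

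- **The 50% belongs to the cut-off alone, under one reading.** This is right. ANOVA or MANOVA does not produce it, and 10.4 does not define the change or say how its two sentences combine. But the alternative readings in Step 2 also leave the error uncontrolled, and some are worse.
- **The 50% is generic and a worst case.** Any roughly symmetric estimate centred on its own margin falls inside it at most half the time, and with SD 0.3 and n = 80 the probability at a 15% fall is already down to 0.04. Both statements are true. But type I error is judged at the boundary of the null, and with a larger SD the probability at a 15% fall stays between 0.15 and 0.29.
- **The SDs are assumed.** This stands for every power and sample-size figure, but not for the 50% ceiling.
- **Sperm count may be only secondary or exploratory.** Sections 3.2 and 10.2 support that; 10.1 does not. Section 1.3 also states a hypothesis on testosterone and gonadotrophins. Even so, the ±10% pair is the only hypothesis in Section 2 and the only one with a rejection rule.

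The sample-size and endpoint-status conflicts are separate defects. They matter here because any power statement for this hypothesis depends on which n is right, and the weight of the conclusion depends on which status holds.

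**Conclusion.** The concern holds and should be fixed before the analysis. Section 10.4 does not test the null in Section 2: the named methods address a different null, and the cut-off carries no error control. Read as a rule on the observed mean, it declares a true 10% change to be no change with probability up to about 0.50, ten times the nominal 0.05. That ceiling rests only on a roughly symmetric estimate. The figures below it and the power of the replacement rule rest on the assumed SDs. Skewed counts or a per-patient definition would move them.

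**What to change.** Replace the decision sentence in 10.4 with wording such as: the null in 2.2 is rejected only if the entire 90% confidence interval for the week-26 versus baseline change in sperm count lies within the ±10% margin (two one-sided tests, each at 5%); ANOVA and MANOVA results are descriptive.

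State in advance:

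1. The variable and scale. Say whether sperm count means concentration or total count (10.2 lists concentration and volume). Choose mean percent change with limits −10% to +10%, or a ratio of geometric means with limits 0.90 to 1.10.
2. How a zero count is handled, since a log ratio cannot use it and 8.1 mentions azoospermia, and how missing week-26 samples are handled, given the intention-to-treat statement in 5.3.
3. Which samples count as baseline and week 26. The calendar in section 12 has semen analyses at Visits 1 and 2 and at Visits 6 and 7. Average each pair only if Visit 1 is confirmed to follow washout (6.1, 7.3) and Visit 7 to be on treatment. The latter is unclear from a 24-week course (4.2) first dispensed at week 2. Otherwise name one post-washout, pre-dose sample and Visit 6.
4. The assumed SD, its source and the resulting power, after 40 and 80 are reconciled.
5. One status for sperm count across 3.2, 10.1 and 10.2.

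The rule itself costs only wording and needs no new data. The real cost is that the trial may be inconclusive. The sponsor should justify an SD near 0.3 with 80 evaluable men, enlarge the trial, or state now that the interval will be reported as an estimate and may not settle the question.

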5.3 Cancellation Guidelines

The following are reasons for withdrawal of subjects from the study:

- A subject does not meet the eligibility criteria; (the subject will be considered a screen failure).
- A subject withdraws consent,
- A subject dies during protocol participation from causes other than the study treatment (not due to adverse events) or
- A study investigator decides the subject should be withdrawn from the study (e.g. subject non-compliance)

Regardless of reason for withdrawal, an intention to treat analysis will be performed.

All subjects who either screen fails, is withdrawn from the study or has completed all visits should be de-enrolled from the research database within 48 hours.

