12. STUDY CALENDAR

| Visit #, Time | Visit 1 (Week 1) Screening | Visit 2 (Week 2) | Visit 3 (Week 6) | Visit 4 (Week 14) | Visit 5 (Week 15) | Visit 6 (Week 26) | Visit 7 (Week 27) |
|--------------------------------------|-------------------------------|---------------------|---------------------|----------------------|----------------------|----------------------|----------------------|
| Medical & Urological History | • | | | | | | |
| Physical Examination & Questionnaire | • | | | • | | • | |
| Informed Consent | • | | | | | | |
| Inclusion & Exclusion Criteria | • | | | | | | |
| Blood Analysis (FSH, LH, T, E) | • | | • (Only T) | • | • (Only T) | • | • (Only T) |
| Semen Analysis | • | • | | • | • | • | • |
| Drug dispensing | | • | | • | | | |

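### The sperm-count analysis names ANOVA and MANOVA with no subject effect, set of visits or missing-sample rule; one permitted reading loses the within-man pairing and another leaves out men with an incomplete series

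*Combined protocol and SAP*

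**What the plan says.** - Section 10.4 gives the method as "Change in sperm count will be analyzed using the ANOVA and MANOVA" and the decision rule as "A change in $< \pm 10\%$ will be reject the null hypothesis". It states no factor, subject term, covariance structure, set of visits or handling of missing samples. The next method sentence, on LH, FSH, E and testosterone, does mention repeated measures; the sperm sentence does not.
- Section 2.1 states the hypothesis of interest: "Natesto™ will not change sperm count by $\pm 10\%$ from baseline". This is a claim of no material change within men.
- In the section 12 calendar, the row "Semen Analysis" is marked at Visits 1, 2, 4, 5, 6 and 7 (weeks 1, 2, 14, 15, 26 and 27). Section 3.2 names only three time points: baseline, week 14 and week 26. Nothing says how the two samples around each time point are combined.
- Section 5.3 promises: "Regardless of reason for withdrawal, an intention to treat analysis will be performed". It gives no method for data that are missing.
- The sample size is given as "TOTAL SAMPLE SIZE: 80" in section 10.3, but section 4.1 has "A total of 40 patients with a diagnosis of idiopathic hypogonadism".

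**The concern.** Sperm counts vary widely between men, and repeated counts from one man are correlated. The question is about change within a man, so the analysis has to remove the between-man spread. A one-way ANOVA with visit as the factor leaves that spread in the error term. MANOVA and classical repeated-measures ANOVA remove it, but in standard form they use only men with every sample that enters the analysis. An ANOVA of change scores across the follow-up visits would ask only whether those visits differ from each other, so an equal fall at weeks 14 and 26 would give no signal.

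The plan allows all of these and does not choose. The choice affects both the standard error of the sperm-count change and which men contribute to it. It could also be made after the data are seen.

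**Working it through.** **What can be reproduced.** Section 10.4 has power calculation in its title but gives no power, SD, correlation or dropout rate. Neither 80 nor 40 can therefore be reproduced. The SDs, correlations and missing rates below are assumptions. Counts are on the log scale, and a sustained 20% loss is ln(0.8) = −0.223 at both week 14 and week 26.

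**1. Visits as independent groups against a paired contrast (nothing missing)**

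For two visits with total SD s and within-man correlation ρ:
- unpaired SE = s√(2/n)
- paired SE = s√(2(1−ρ)/n)
- ratio = 1/√(1−ρ), which is 1.41, 1.83 and 2.24 at ρ = 0.5, 0.7 and 0.8.

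*Set A: between-man SD 1.0, within-man SD 0.4.* ρ = 1/(1 + 0.16) = 0.86. The SD of a within-man difference is 0.4√2 = 0.566. At n=80 the paired SE is 0.566/√80 = 0.0632, and 0.223/0.0632 = 3.53, which gives 94% power at two-sided 5%.

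*Set B: log-SD 0.8, ρ = 0.7.* The SD of a difference is 0.8√(2 × 0.3) = 0.620. At n=80 the paired SE is 0.620/√80 = 0.0693, and 0.223/0.0693 = 3.22, which gives 89%.

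The one-way ANOVA over three visits was simulated (4,000 trials per setting).

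| Assumptions | n | True loss | Independent-groups ANOVA | Paired week 26 minus baseline |
|---|---|---|---|---|
| Set A | 80 | 20% | about 1% | 94% |
| Set A | 80 | 30% | 49% | about 100% |
| Set A | 40 | 20% | under 1% | 68% |
| Set B | 80 | 20% | 27% | 89% |
| Set B | 40 | 20% | 5% | 60% |

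The independent-groups test is also far off its nominal level. With no true change (set B, with the missing data of step 3) it rejected in about 0% of trials instead of 5%.

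**2. Change scores across follow-up visits only**

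With an equal loss at weeks 14 and 26, a within-man comparison of the two change scores rejected in 5–6% of simulated trials. That is the false-positive rate.

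**3. Complete-case MANOVA or repeated-measures ANOVA**

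An enrolled man must have a screening semen result (section 6.2, exclusion 5). Only the other five samples can be missing. If samples are missed independently:
- 95% obtained: 0.95⁵ = 0.774, so 80 × 0.774 = 62 men remain
- 90% obtained: 0.90⁵ = 0.590, so 80 × 0.590 = 47 men remain.

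The cost in power is smaller than these counts suggest. Under set A with six samples and a 20% loss, complete-case MANOVA detected the loss in 97% of trials with 59 men and in 88% with 43. Those are the counts if the screening sample could also be missing (80 × 0.95⁶ = 58.8; 80 × 0.90⁶ = 42.5), so 62 and 47 men do no worse.

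Under set B with three visits, 10% missing at week 14 and 15% at week 26, and a 20% loss:

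| n | Independent-groups ANOVA | Complete-case MANOVA | Bound with nothing missing |
|---|---|---|---|
| 80 | 28% | 81% | 92% |
| 40 | 6% | 48% | 62% |

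These runs assume samples missing completely at random. They measure lost precision only and say nothing about bias from selective withdrawal.

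**The case against.** The text states neither extreme. It does not say that visits are independent groups or that incomplete men are deleted. The words change and from baseline suit a within-man analysis, and repeated-measures ANOVA with MANOVA is the classical pair for one. This stands: the fault is an under-specified method that permits poor analyses, not a declared wrong one.

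Three stronger readings are tempting, and the documents do not support them.

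- *A real loss is likely to be missed.* This follows for independent-groups ANOVA with losses near 20%, and in several settings at n=40. It does not follow in general. With n=80 and a 30% loss, that ANOVA had 61–99% power over log-SDs of 0.7–1.0 and correlations of 0.3–0.8. Complete-case MANOVA loses only a modest amount of power. The 1% figure also depends on a high assumed correlation (0.86).
- *The fault favours a finding of no change under any decision rule.* The stated rule is a change within ±10%, not P above 0.05. Applied to a point estimate, that rule does not use the standard error. Applied to a confidence interval, an inflated standard error makes no change harder to conclude. The bias arises only if non-significance is taken as no change, which section 10.4 does not say.
- *Intention to treat is contradicted.* Section 5.3 sets no missing-data method and section 10.4 states no deletion. The conflict appears only if a complete-case method is used.

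The count of complete men also depends on which samples enter the analysis. If the two samples around each time point are averaged, far fewer men are incomplete.

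One reply remains. Section 10.4 mentions repeated measures for the hormones only, and it refers to groups A and B, which are defined nowhere. It cannot be relied on to imply a within-man model for sperm count.

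**Conclusion.** The point holds as an under-specified analysis for which a better method is available at no cost in data; it should be fixed. The size depends on the reading taken. Visits compared as independent groups would lose most of the power for a sustained 20% loss at n=80: about 1% against 94%, or 27% against 89%, under the two sets of assumptions. Complete-case MANOVA or repeated-measures ANOVA would usually cost little power. It would leave out about 18 of 80 men (80 − 62) at 95% completeness per sample, or 33 (80 − 47) at 90%. That fits poorly with intention to treat, and the result would be biased if men with falling counts were the ones who left.

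The SDs, correlations and missing rates are assumed because the documents give none. The larger weakness is that no equivalence test is attached to the ±10% margin. This change does not cure that, although any interval set against the margin needs a correct within-man standard error and a defined set of men.

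**What to change.** Replace the sperm-count sentence in section 10.4 with wording such as:

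> Log sperm count will be analysed with a linear mixed model using every available sample, with a random man effect and period (baseline = Visits 1 and 2; week 14 = Visits 4 and 5; week 26 = Visits 6 and 7) as fixed effect. The result is the week-26/baseline ratio with its confidence interval, judged against the stated ±10% margin. No man is dropped for a missing sample, and a sensitivity analysis for missing data will be reported.

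The log scale turns the contrast into a ratio, which matches a percentage margin. Three details need a line each:
- how a zero count enters on the log scale, since section 8.1 mentions azoospermia;
- confirmation that the Visit 2 sample is taken before the first dose, since drug is dispensed at that visit;
- a man-by-period random term if samples a week apart prove more alike than samples months apart, because otherwise the standard error will be too small.

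The cost is SAP wording and a little more analysis work, with no extra visits or samples. The model assumes data missing at random, which is why the sensitivity analysis is included. The two sample sizes, 40 and 80, must be reconciled, and the equivalence test against ±10% must be specified separately.

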3. OBJECTIVES

3.1 Primary Efficacy Objective

Primary outcomes will be changes in LH, FSH, testosterone, estrogen, and quality of life from baseline, 14 weeks ± 7 days and 26 weeks ± 7 days.

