7.3 Pre-Treatment Procedures and Evaluations

Upon evaluating the inclusion/exclusion criteria, patients will be recruited to the study. Patients will be instructed to stop any use of androgen replacement for 4 weeks prior to first treatment session and refrain from using any other androgen replacement therapy option during the study. After the washout period and before the first treatment session, patients will answer the IIEF-EF and SF-36 questionnaires for baseline evaluation.

7.4 Follow-Up Procedures and Evaluations:

Follow-up visits will be conducted at week 14+/- 7 days and 26+/- 7 days, these visits shall include:

- Measuring IIEF-EF and SF-36 scores of patients at the clinic
- Taking serum FSH, LH, E, and total Testosterone levels
- Semen analysis
- Reporting and recording adverse events at every follow-up visit.

Additional determinations of total serum testosterone will be performed periodically at every follow up visit, beginning one month after initiation of therapy. Additional semen analysis will be performed at weeks 15+/- 7 days and 27+/- 7 days.

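### The hormone analysis in section 10.4 is not defined: a one-sample t-test has no repeated-measures form, and the false-positive rate depends on how the sentence is read

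*Combined protocol and SAP*

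**What the plan says.** Section 10.4 gives the whole inferential plan for the hormones in one sentence: "LH, FSH, E and Testosterone levels will be analyzed using one-sample t-test with repeated measures throughout the study". The significance level in that section is 5%; sidedness is not stated.

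The outcome is defined elsewhere, in two ways:

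- Section 3.1: "Primary outcomes will be changes in LH, FSH, testosterone, estrogen, and quality of life from baseline, 14 weeks ± 7 days and 26 weeks ± 7 days".
- Section 10.1: "The primary endpoint will be change in FSH, LH, Testosterone, and Semen Analysis after 6 months of treatment of Natesto".

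Both define the outcome as change. They differ on timing (two visits against one), and only section 3.1 includes estrogen.

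Section 7.4 sets the main visits: "Follow-up visits will be conducted at week 14+/- 7 days and 26+/- 7 days". It also provides for extra testosterone measurements. In the study calendar (section 12), the row "Blood Analysis (FSH, LH, T, E") shows one draw before dispensing, at Visit 1. After dispensing at Visit 2 it shows LH, FSH and E at weeks 14 and 26, and testosterone at weeks 6, 14, 15, 26 and 27.

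**The concern.** A one-sample t-test compares the mean of independent values, one per subject, with a fixed number. It has no repeated-measures version. An analyst given the section 10.4 sentence would have to decide four things that the plan leaves open: whether the response is a level or a change, what it is compared with, which visit or visits count, and how several values from one man are handled.

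Three readings are possible:

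1. All post-baseline values are pooled as if each came from a different man. The standard error is then too small.
2. Levels at a visit are tested against the baseline mean as if it were a known constant. This ignores the sampling error of the baseline mean and discards the pairing.
3. Each man's change at a visit is tested against zero. This is the paired t-test, and it is valid.

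The sentence is the only inferential analysis of the primary hormone outcomes. Unless it is settled beforehand, the choice could be made after the data are seen, among analyses with materially different error rates.

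**Working it through.** The documents give no power, standard deviation, within-man correlation or error rate for the hormone tests, so there is no stated figure to reproduce. The check asks what error rate each reading would give.

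**Inputs from the documents.** Nominal alpha is 0.05 (section 10.4), taken as two-sided. Post-baseline draws per man are m = 2 for LH, FSH and E, and m = 5 for testosterone (section 12). The sample size is 40 in section 4.1 and 80 in sections 6.3 and 10.3; the simulated error rates below are nearly the same for both.

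**Assumed.** The correlation rho between two changes in the same man is not given. If all visits have equal variance s² and equal pairwise correlation r, two changes from one shared baseline have covariance s²(1 − r) and variance 2s²(1 − r). Their correlation is then 0.5 whatever r is. That makes 0.5 a reasonable central value, but it remains an assumption, so a range is shown.

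**Reading 1, pooled as independent rows.** The variance of the mean is understated by the factor DE = 1 + (m − 1) × rho, and the actual error is 2 × (1 − Φ(1.96/√DE)).

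- m = 2, rho = 0.5: DE = 1.5; 1.96/√1.5 = 1.60; error 11.0%.
- m = 5, rho = 0.5: DE = 3.0; 1.96/√3.0 = 1.13; error 25.8%.

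| Assumed rho | m = 2 | m = 5 |
|---|---|---|
| 0.1 | 6.2% | 9.8% |
| 0.3 | 8.6% | 18.6% |
| 0.5 | 11.0% | 25.8% |
| 0.7 | 13.3% | 31.5% |
| 0.9 | 15.5% | 36.1% |

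A simulation with a shared baseline (20,000 trials per setting; n = 40 and 80; r = 0.3 and 0.7) gave 10.7% to 11.1% for m = 2 and 25.5% to 26.3% for m = 5.

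**Reading 2, levels against the baseline mean as a constant.** Let r be the correlation between a man's baseline and follow-up levels, with equal variances. The true variance of the difference in means is 2(1 − r) times the variance that the test assumes. The error is 2 × (1 − Φ(1.96/√(2(1 − r)))).

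- r = 0.3: 1.96/√1.4 = 1.66; error 9.8%.
- r = 0.7: 1.96/√0.6 = 2.53; error 1.1%.

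This reading can err in either direction.

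**Reading 3, each man's change.** In the same simulation, a test at one visit fixed in advance gave 4.8% to 5.2%, and a test of each man's mean change gave 4.7% to 5.3%. Both are the nominal 5%. If every visit were tested and any significant result counted, the error was about 9% (m = 2) or 18% to 19% (m = 5). That is multiplicity, not ignored correlation, but the sentence does not rule it out.

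**The case against.** The strongest reply is that nothing in the plan says visits are pooled. The mention of repeated measures may mean that the correlation is to be handled. Since sections 3.1 and 10.1 define the outcome as change, a one-sample t-test on each man's change is a natural reading, and it is valid. A reader might infer from the arithmetic that the planned hormone P values carry an 11% to 26% false-positive rate. The documents do not support that: those figures are conditional on pooling and on an assumed correlation. This part of the reply stands.

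Three further points also have force:

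- The 26% needs all five testosterone draws. Section 3.1 limits the outcome to weeks 14 and 26, and section 10.1 to six months. On those definitions m is 2 or 1. Only the reference in section 10.4 to the whole study period brings in all five.
- The value 0.5 requires equal variances. Entry requires two testosterone values below 350 ng/dL (section 6.1), which may narrow the baseline spread. If, as an illustration, the on-treatment SD were twice the baseline SD and levels were independent, changes would correlate 1/(1 + 4) = 0.2. Pooling would then give about 7% (m = 2, DE = 1.2) or 14% (m = 5, DE = 1.8).
- The direction of harm differs by hormone. Section 1.3 expects testosterone to rise and LH and FSH to show no significant impact. A standard error that is too small makes a testosterone rise easier to show and works against a finding of no LH or FSH impact.

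The reply does not remove the point. The valid reading holds 5% only for a visit named in advance, and sections 3.1, 10.1 and 10.4 point to different visits. Nor does the wording itself select that reading, because it refers to levels.

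**Conclusion.** The point holds as a failure of specification. The sentence cannot be run as written, it does not match the outcome defined in sections 3.1 and 10.1, and two of its three readings give wrong standard errors. The false-positive rate would be about 5% for a paired test at one named visit. It would be 9.8% or 1.1% for levels against a constant, at within-man correlations of 0.3 and 0.7. It would be about 11% (two draws) or 26% (five draws) for pooled rows at correlation 0.5. Pooling exceeds 5% at every correlation from 0.1 to 0.9, but whether it would be done is unknown.

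The firm part is the mismatch between test, response and outcome. The sizes rest on assumed correlations and equal variances. Because a valid reading exists and the repair is simple, this is a should-fix. The absence of a no-change margin for LH and FSH is a separate matter.

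**What to change.** Replace the hormone sentence in section 10.4 with a within-man analysis of change from baseline. Suggested content:

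- For each of LH, FSH, E and testosterone, the main contrast is week 26 minus baseline (section 10.1). The week-14 change is also reported (section 3.1). Each has a 95% confidence interval.
- The analysis is a mixed model for repeated measures, with baseline and scheduled visits as outcomes, visit as a categorical effect and the within-man covariance modelled. Name a simpler fallback structure in case the model does not converge. This matters most for testosterone: six time points with unstructured covariance need 6 × 7/2 = 21 parameters, from 40 or 80 men.
- Testosterone at weeks 6, 15 and 27 is supportive.
- A log scale is optional.

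The minimum alternative is a paired t-test on the week-26 change. It holds about 5% but uses only men measured at week 26, which sits less well with the intention-to-treat commitment in section 5.3. The mixed model uses all observed values.

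The cost is SAP wording and slightly more programming, with no new data. Compared with a pooled analysis, P values become larger. That is less favourable for showing a testosterone rise, but not for the hypothesis of no LH or FSH impact.
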